Evolocumab in Patients With Acute MI NCT04082442 7/14/2021

Evolocumab in Patients with Acute Myocardial Infarction (NCT04082442)

Study Statistics

Cover Sheet

Title: Evolocumab in Patients with Acute Myocardial Infarction: A Double-blind, Prospective, Randomized, Placebo-Controlled Study

Study Type: Interventional (Randomized, Double-Blind, Placebo-Controlled)

Population: Patients with acute myocardial infarction receiving high-intensity statin therapy

Sample Size: 100 participants (50 per arm: Evolocumab vs. Placebo)

Primary Outcome: Percent change in LDL-cholesterol (LDL-C) from baseline to 30 days

Key Secondary Outcome: Change in myocardial inflammation measured by FDG-PET (mean Standardized Uptake Value, SUV) from baseline to 30 days

Analysis Population: All randomized participants with evaluable baseline and follow-up data

Primary Endpoint Analysis

Endpoint Definition: Difference in the mean percent change in LDL-C from baseline (prerandomization) to 30 days in the evolocumab and placebo groups.

Statistical Method:

- Mean ± SD LDL-C at baseline and 30 days will be summarized for each group.
- Between-group comparisons will use an independent-samples t-test (two-sample test of means).
- Percent change will be calculated as: ((LDL-C30d LDL-Cbaseline) / LDL-Cbaseline) × 100.
- Two-sided p < 0.05 will indicate statistical significance.
- Results will also be presented as mean differences with 95% confidence intervals.

Power Considerations: Assuming baseline LDL-C \approx 110 mg/dL, 50% reduction with standard statin therapy, and an additional 50% reduction with evolocumab, a sample size of 50 per group provides >99% power (one-sided α = 0.05) to detect a 13.5 mg/dL absolute LDL-C difference.

Secondary Endpoint Analysis

Endpoint Definition: Change in inflammation quantified as mean FDG-PET Standardized Uptake Value (SUV) from baseline (index hospitalization) to 30 days in the evolocumab and placebo groups.

Statistical Method:

- For within-group change: paired t-test or Wilcoxon signed-rank test (if non-normal).
- For between-group comparisons: independent-samples t-test or Mann-Whitney U test.
- Data will be presented as mean ± SD and mean difference (95% CI).
- Significance defined as two-sided p < 0.05.

Power Considerations: Assuming mean \pm SD = 35.4 \pm 18.1 (Ripschler et al.), with 50 participants per arm, there is 80% power to detect a 30% difference in mean SUV between groups. For vascular inflammation (TBR, target-to-background ratio), published differences of 10–15% yield >88–99% power for n = 50 per group.

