This is a phase 2, double-blind, randomized, placebo controlled clinical trial of 420 mg evolocumab administered subcutaneously using an autoinjector/pen in NSTEMI and STEMI patients during early hospitalization at the Johns Hopkins Hospital and the Johns Hopkins Bayview Medical Center. The placebo and evolocumab will be given exactly the same way with the same Amgen provided device. All participants will receive standard care for NSTEMI and STEMI, including, as appropriate, high dose statin, aspirin, beta blocker, an angiotensin converting enzyme inhibitor or angiotensin receptor blocker, as well as angiography and reperfusion. High dose statin therapy consists of atorvastatin 40mg or 80mg or rosuvastatin 20mg or 40mg per the most recent ACC/AHA guidelines. [41] After signing informed consent, subjects will be randomized to receive one dose of evolocumab or matching placebo subcutaneously. Research blood samples for lipid profile, endothelial function, and inflammatory markers, and PET imaging assessment of myocardial and vascular inflammation as well as any clinically indicated echocardiographic studies for left ventricular function will also be obtained. Additionally, in a subset of patients we will obtain cardiac MRI studies. An independent Data and Safety Monitoring Committee will review all potential side effects and clinical outcomes during the six months of follow-up.

FDG/PET scans are not performed at Hopkins Bayview. If participants enrolled at that site are transferred to Hopkins Hospital for clinical care, and the scan can be performed during that hospitalization, it will be done so. For other patients, i.e. those discharged home from Bayview, or Hopkins patients who could not undergo the scan during their admission because of scheduling issues, the first scan will be performed on an outpatient basis. In those instances a car service will be arranged to transfer the participants to and from JHH and they will have three outpatient visits, for the initial and the follow-up 30 day scans, and for the six-month visit.

After hospital discharge, we will send a letter to the participant's physician(s) to inform them that the participant was enrolled in the study and that lipid values during the 4-5-week period after study drug administration may reflect the impact of evolovumab if the participant is randomized to that agent. The letter is attached in the supplemental study documents.

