For calculation of power for the co-primary endpoint of LDL-C, we anticipate median baseline presentation LDL-C of 110~(90-130)~mg/dL in our patient population. This number is informed by prior ACS trials as well as local experience with the STEMI population treated at the Johns Hopkins Hospital (with approximately 25%-35% of the population already on baseline statin therapy). We expect this LDL-C value to be reduced by approximately 50% by high intensity statin therapy in the standard treatment arm (i.e. to an LDL-C of 55 (40-70) mg/dL at 30 days). We anticipate a further 50% lowering of LDL-C at 30 days after the administration of evolocumab (i.e. to an LDL-C of 28 (14 – 42) mg/dL. As is shown below (Table 1), using a one-sided p-value of 0.05, the study has nearly 100% power to detect this difference, and will have 80% power to detect an absolute LDL-C reduction of only 13.5 mg/dL (24% reduction in LDL-C at 30 days). Additionally, Table 2 presents the expected mean \pm SD baseline and 30-day LDL-C levels and the expected percent changes in the mean LDL-C in the placebo and evolocumab arms.

Table 1:

		Anticipated	Estimated	Detectable
N in each group	Median (IQR)	Percent	Power to	Point
	LDL-C in ACS	LDL-C	Detect a	Estimate at
	Population at	Reduction in	50%	>80%
	baseline	the	Additional	Power
		Standard of	LDL	
		Care Arm	Lowering	
N = 50	110 (90-130)	50% (40 –	99+%	-13.5 mg/dL
		60%)		

Table 2: Expected mean \pm SD LDL-C levels at baseline and thirty-days and the percent change from baseline to 30 days in the placebo and evolocumab groups.

Groups:		LDL-C, mg/dl		% change from	
		Baseline, mean (SD)	30 day, mean (SD)	baseline, mean (SD)	
High	+Placebo	110 (±14)	55 (±11)	-50 (±12)	
dose statin	+Evolocum ab		28 (±10)	-75 (±14)	

For the co-primary FDG-PET assessed myocardial inflammation endpoint, appropriate data necessary for power calculations are currently unavailable. With 50 patients in each arm, applying the overall mean (SD) of 35.4 (18.1) from Ripschler et al [38] as a baseline estimate, we will have 80% power to detect a 30 % difference in FDG-PET assessed myocardial inflammation between the evolocumab and placebo groups.

Secondary Endpoint:

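### The primary LDL-C analysis ignores prior statin use, expected in 25%-35% of patients, and so gives up precision that one baseline covariate could recover

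*SAP*

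**What the plan says.** The SAP cover sheet describes the trial as "Population: Patients with acute myocardial infarction receiving high-intensity statin therapy". Protocol section 4.a is looser: "All participants will receive standard care for NSTEMI and STEMI, including, as appropriate, high dose statin". No criterion in sections 5.1 or 5.2 requires a statin.

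Protocol section 9 (Sample Size Considerations, Primary endpoints) supports its baseline median of 110 mg/dL with earlier trials and local experience, "with approximately 25%-35% of the population already on baseline statin therapy". It then says: "We expect this LDL-C value to be reduced by approximately 50% by high intensity statin therapy in the standard treatment arm". For the active arm: "We anticipate a further 50% lowering of LDL-C at 30 days after the administration of evolocumab". Table 2 turns this into one mean (SD) percent change per arm, -50 (12) on placebo and -75 (14) on evolocumab, both under a high-dose statin label. The SAP power paragraph repeats the single 50%.

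For the primary endpoint the SAP states: "Between-group comparisons will use an independent-samples t-test (two-sample test of means"). It includes no covariate. The only adjustment variable named in the protocol is the time from hospitalisation to study drug, in the section 9 sample-size text. Neither document stratifies by, or adjusts for, prior statin use.

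**The concern.** In this plan the statin produces the entire assumed placebo fall. A patient whose presentation LDL-C already reflects a statin would plausibly fall by less than a patient new to the drug. If so, each arm mixes two groups with different expected percent changes, and the t-test counts the difference between them as unexplained error.

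What is at stake is the precision of the estimate, not the test. The SAP promises a mean difference with a 95% CI, and with power this high that interval is the main product of the primary analysis. Two things follow from the mixture: the interval is wider than it needs to be, and a chance imbalance in prior statin use between arms of 50 moves the point estimate. The planning figure of -50% for placebo also shows no allowance for prior users.

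**Working it through.** **Inputs.** From the documents: n = 50 per arm; percent change -50 (SD 12) and -75 (SD 14) (protocol Table 2); share of prior users p = 0.25 to 0.35 (protocol section 9). Assumptions, not in the documents: (a) on placebo, prior users fall by g points less than new users, with g = 10, 20, 30 or 50 (g = 50 means no further fall); (b) evolocumab halves whatever LDL-C remains, as the protocol assumes, so the gap in that arm is g/2; (c) the Table 2 SDs hold within each statin group.

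**The plan's own figure.** SE = sqrt((12² + 14²)/50) = sqrt(6.8) = 2.61, so the 95% CI half-width is 1.96 × 2.61 = 5.1 points. A 25-point difference is 25/2.61 = 9.6 SEs. The stated 99+% power reproduces, one- or two-sided.

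**Unadjusted analysis with the mixture.**
- Placebo SD = sqrt(12² + p(1-p)g²)
- Evolocumab SD = sqrt(14² + p(1-p)(g/2)²)
- SE = sqrt((sum of the two variances)/50)
- Placebo mean = -50 + pg; arm difference = 25 + pg/2

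Example, p = 0.30 and g = 20: placebo variance 144 + 0.21 × 400 = 228; evolocumab variance 196 + 0.21 × 100 = 217; SE = sqrt(445/50) = 2.98; ratio 2.98/2.61 = 1.14.

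| g (points) | Placebo mean, p = 0.25 to 0.35 | Unadjusted SE | CI wider than Table 2 implies | Arm difference |
|---|---|---|---|---|
| 10 | -47.5 to -46.5 | 2.70-2.71 | 3-4% | 26.3-26.8 |
| 20 | -45.0 to -43.0 | 2.95-3.01 | 13-16% | 27.5-28.5 |
| 30 | -42.5 to -39.5 | 3.32-3.45 | 27-32% | 28.8-30.3 |
| 50 | -37.5 to -32.5 | 4.30-4.58 | 65-76% | 31.3-33.8 |

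**Power.** The difference is at least 7 SEs in every row (31.25/4.30 = 7.3 is among the smallest), so two-sided power exceeds 99.9%. In a harsher case, with a 50-point gap in both arms and a constant 25-point effect, the SE is 5.05-5.44 and power is still 99.6-99.9%.

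**What a covariate recovers.** In a model with arm and prior statin use, the common slope averages the two gaps, g and g/2, to 0.75g. That leaves 0.25g unexplained in each arm, so adjusted SE = sqrt((144 + 196 + 2p(1-p)(0.25g)²)/50). At p = 0.30:
- g = 20: sqrt((340 + 10.5)/50) = 2.65, against 2.98 unadjusted
- g = 50: sqrt((340 + 65.6)/50) = 2.85, against 4.46 unadjusted

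A simulation of 10,000 trials, with the statin group and its interaction with arm in the model, gave 2.64 adjusted against 2.97 unadjusted (g = 20) and 2.86 against 4.40 (g = 50). The mean estimate was the same with and without adjustment (-27.97 in both; -32.45 and -32.40).

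**Chance imbalance.** The SD of the between-arm difference in the share of prior users is sqrt(2p(1-p)/50) = 0.087-0.095, about 9 percentage points. Multiplied by the average gap of 0.75g, a 1-SD imbalance at p = 0.30 (0.092) shifts the estimate by about 0.092 × 15 = 1.4 points at g = 20 and 0.092 × 37.5 = 3.4 points at g = 50.

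**The case against.** The strongest reply is that the size of the loss rests on a response the documents never give. They state neither the dose nor the adherence of prior users, nor how far their LDL-C would fall. Table 2 presents its SDs as whole-arm values, and they may already contain some of the mix. On that reading p(1-p)g² cannot exceed 12² = 144, so g is at most 12/sqrt(0.1875) = 27.7 points at p = 0.25 and 12/sqrt(0.2275) = 25.2 at p = 0.35. The 30- and 50-point rows then drop out. This stands as a limit on size, but it does not remove the gain. At p = 0.30 and g = 20 the within-group variances become 144 - 84 = 60 and 196 - 21 = 175, and the SE falls from 2.61 to sqrt(235/50) = 2.17, about 17% narrower (about 15%, SE 2.22, after adding the 10.5 for the unequal gaps).

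The t-test is also valid as planned. Its SE already includes chance imbalance, so imbalance is not a further error on top of the CI. That stands: adjustment makes the estimate tighter but does not rescue an invalid test.

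A reader might infer that the SAP has every patient starting a statin. Its word is receiving, which fits a prior user who continues. In protocol section 4.a the qualifier covers a whole list of standard care, and the protocol's Table 2 makes the same simplification. The label is loose wording rather than a departure from the protocol in how the endpoint is analysed.

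Finally, study drug may be given up to a week after presentation (section 5.1), so in-hospital statin may already have lowered some pre-randomisation values. A yes/no flag for pre-admission use would not capture that.

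**Conclusion.** The point holds as a minor precision improvement. The plan expects 25%-35% prior statin users, models one 50% statin fall for all, and leaves a plausible pre-randomisation predictor out of the primary analysis. Under the stated assumptions the unadjusted CI is between 3% and 76% wider than Table 2 implies. The lower rows of that range are as compatible with the documents as the upper ones, and a whole-arm reading of the Table 2 SDs limits the gap to about 25-28 points.

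A reader might go further and infer that the trial is underpowered, that the primary result would be biased, or that a specific gain can be promised. The documents support none of these. Power stays above 99% in every case examined, randomisation prevents expected bias, and the gain cannot be fixed without the response of prior users. No change in sample size follows.

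**What to change.** In the SAP, prespecify the primary analysis as a linear model of percent change in LDL-C on arm, with pre-admission statin use (yes/no) as a covariate, and report the adjusted mean difference with its 95% CI. Keep the two-sample t-test as a sensitivity analysis. An arm-by-statin interaction is optional. Report statin use at baseline and at day 30 by arm.

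Reword the SAP population line so that it matches protocol section 4.a, where high-dose statin is part of standard care given as appropriate. Add a note to the power text that the -50% placebo figure makes no stated allowance for prior users.

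The cost is a few lines of SAP text and no new patients or visits. The one condition is that pre-admission statin use exists as a coded field. The protocol's COVID-19 accommodations list medical history and concomitant therapies but do not name it, so the sponsor should confirm this, or code it from the medical history, before unblinding.

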2.2 Secondary (for the intervention study group)

The secondary objectives are to compare in the evolocumab and placebo groups:

a. Serial serum markers of inflammation, platelet and endothelial cell function, lipids, and myocardial injury, and left ventricular function which will be collected at pre-randomization, during hospitalization, at hospital discharge and at 25-30 days, 6 months and 12 months follow up. In those who are discharged before day 3, and those who are unwilling or unable to return to the hospital, additional samples may be obtained in the out of hospital setting.

The time points of comparison are pre-randomization, during hospitalization, at hospital discharge, and any obtained in the outpatient setting including the 30 days, 6 months, and 12 months samples.

- i. PCSK-9
- ii. Soluble LOX-1
- iii. IL-6, IL-10, IL-12
- iv. hsCRP
- v. platelet function
- vi. LDL-Cholesterol
- vii. HDL-Cholesterol
- viii. Triglycerides
- ix. Total Cholesterol
- x. Apolipoprotein B
- xi. Lipoprotein (a)
- xii. Troponin
- xiii. Pro-BNP
- xiv. HbA1c
- xv. Insulin
- b. The change between hospitalization and thirty day of:
 - i. PET-FDG assessed myocardial inflammation and vascular inflammation in the most diseased segment of aorta or carotid artery. For this outcome, separate analyses will also be performed in those who did and did not undergo the initial PET scan within 48 hours of study drug administration.
 - ii. Echo assessed regional wall motion in the infarct territory
 - iii. Echo assessed global LV function
 - iv. Echo assessed LV systolic and diastolic volumes

The times of collection will be at early hospitalization and 30 days. The time point of comparison will be at 30 days

c. At thirty days:

- i. Comparison of PET-FDG assessment of myocardial inflammation and vascular inflammation in the evolocumab versus placebo group as described in 2.2. b i
- ii. Echo assessed as described in 2.2. b ii-iv
- iii. Angina class
- iv. New York Heart Association functional class
- v. Serum markers as described in 2.2. a

d. At six months

- i. Angina class
- ii. New York Heart Association functional class
- iii. Echo assessment as described in 2.2. b ii-iv

In a subset of participants: The change between early infarction period and six months assessments of Cardiac MRI-assessed adverse remodeling, e.g. LV function and volumes, infarct size and scar quantification

e. At 12 months

Serum markers as described in 2.2 a

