d. Justification of why participants will not receive routine care or will have current therapy stopped.

All participants will receive routine care and will not have current therapy stopped.

e. Justification for inclusion of a placebo or non-treatment group.

Inclusion of a placebo, comparator group is necessary to best determine the safety and efficacy of evolocumab in NSTEMI and STEMI patients. As noted above, evolocumab is not considered "treatment" for this patient population and hence we do not believe there is a "non-treatment" group, or ethical concern by inclusion of a placebo group.

f. Definition of treatment failure or participant removal criteria.

There is no defined "treatment failure." Outcomes of those randomized to evolocumab or placebo will be collected to determine whether the "treatment" was or was not successful in terms of the safety and efficacy outcomes.

Participants are volunteers and may decline continued participation and if so will be removed from any further study procedures. In addition, those who undergo unanticipated coronary bypass surgery will not undergo the second PET study as cardiopulmonary bypass itself is associated with increased inflammation and therefore would confound interpretation of the inflammatory outcomes. We will gather the lipid outcomes in these individuals.

Early stopping rules:

The study will be stopped early on the recommendation of the Data Safety and Monitoring Committee or if there is any new published information regarding the safety of the study drug or the study procedures.

g. Description of what happens to participants receiving therapy when study ends or if a participant's participation in the study ends prematurely.

Participants will only receive one dose of the study drug on the day of enrollment and thus will not be receiving any study related therapy when the study ends or if the participant's participation in the study ends prematurely.

Study Procedures (for the observation study group)

- a. Blood draws:
 - i. Participants will undergo 4 blood draws of about 3-4 tablespoons each to measure lipoprotein (a) [Lp(a)], cholesterol levels, and thrombotic and inflammatory markers and mediators. The first blood draw will be at the time the participant presents to the hospital, followed by an additional blood draw during the inpatient stay, a blood draw at a 30-day follow-up visit and a final blood draw at a 6 months follow-up visit.

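### The primary LDL-C analysis is observed-case: randomised patients without a 30-day value drop out, and earlier post-dose LDL-C and the baseline covariate go unused

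*SAP*

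**What the plan says.** The SAP cover sheet gives one analysis population: "All randomized participants with evaluable baseline and follow-up data". It does not define evaluable. Under Primary Endpoint Analysis the endpoint is "Difference in the mean percent change in LDL-C from baseline (prerandomization) to 30 days in the evolocumab and placebo groups", with percent change calculated from the 30-day and baseline values. On the test, the SAP says "Between-group comparisons will use an independent-samples t-test (two-sample test of means", and "Two-sided p < 0.05 will indicate statistical significance". Baseline LDL-C enters only through the percent-change formula, not as a covariate.

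Protocol section 2.2.a lists LDL-C among the serum markers, "which will be collected at pre-randomization, during hospitalization, at hospital discharge and at 25-30 days, 6 months and 12 months follow up". It also allows samples outside the hospital for patients discharged before day 3 or who will not or cannot return. Section 4.f says: "Participants are volunteers and may decline continued participation and if so will be removed from any further study procedures". The same section keeps collecting lipids after unanticipated bypass surgery but omits the second PET scan in those patients.

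For the intervention study, neither document gives an imputation rule, a repeated-measures model, a missing-data sensitivity analysis or a dropout allowance. Mixed-effects and GEE models on all available time points are planned only for the observation study (Protocol section 10).

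**The concern.** The population wording does not itself name day 30. The restriction follows from combining it with the 30-day formula and a test that needs one value per patient. Patients who die, withdraw or give no sample by about day 30 are therefore removed after randomisation. If the reasons for missing values differ between arms, the remaining groups are no longer comparable by design.

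The trial's main product is an effect estimate with a 95% confidence interval, so bias in that estimate matters even when the p-value is safe. Much of the information needed to limit it will already have been collected.

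**Working it through.** **Inputs.** Protocol Table 2: percent change −50 (SD 12) on placebo and −75 (SD 14) on evolocumab; 30-day LDL-C 55 (SD 11) and 28 (SD 10) mg/dL. There are 50 patients per arm. Each arm is assumed to lack a 30-day value in a share d of patients, with d from 5% to 30%, because the documents give no rate.

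**1. The plan's own power.** The protocol says "using a one-sided p-value of 0.05, the study has nearly 100% power to detect this difference".
- Common SD for percent change: √((12² + 14²)/2) = 13.04 points.
- Standardised difference at n = 50: 25 / (13.04 × √(2/50)) = 9.59. Power is above 99.9%, one- or two-sided, so the figure reproduces.
- The SAP claims "a sample size of 50 per group provides >99% power (one-sided α = 0.05) to detect a 13.5 mg/dL absolute LDL-C difference". With SD √((11² + 10²)/2) = 10.51 mg/dL, 13.5 / (10.51 × 0.2) = 6.42, which is also above 99.9%.
- The protocol attaches only 80% power to the same 13.5 mg/dL. That is a separate inconsistency to reconcile and does not affect this point.

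**2. Effect of missing values on power and precision.** With n = 50(1 − d), two-sided 0.05, and CI half-width 1.96 × 13.04 × √(2/n):

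| d | n per arm | Power for 25 points | Half-width (points) |
|---|---|---|---|
| 5% | 47.5 | >99.9% | 5.2 |
| 10% | 45 | >99.9% | 5.4 |
| 20% | 40 | >99.9% | 5.7 |
| 30% | 35 | >99.9% | 6.1 |

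**3. Possible bias.** Let missing patients have mean change m0 on placebo and m1 on evolocumab. The all-randomised difference is

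[(1 − d)(−75) + d·m1] − [(1 − d)(−50) + d·m0],

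while the observed-case estimate stays at −25. The assumed shift is 30 points:

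| Missing patients | d = 10% | d = 20% | d = 30% |
|---|---|---|---|
| Evolocumab −45, placebo −50 | −22 | −19 | −16 |
| Evolocumab −75, placebo −20 | −28 | −31 | −34 |
| Evolocumab −45, placebo −20 | −25 | −25 | −25 |

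For example, row 1 at 10%: 0.9 × (−75) + 0.1 × (−45) = −72, and −72 − (−50) = −22. The error is d × 30, so 3, 6 or 9 points. Its sign depends on the arm, and it vanishes when both arms shift equally at equal rates.

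**4. Whether earlier values help.** A large-sample simulation made 30-day values missing in the evolocumab arm only, driven by an early post-dose value. The missing share was 10% to 30% and the correlation between early and 30-day values 0.3 to 0.7. The true difference was −25. The observed-case estimate ran from −25.4 to −27.5; an analysis using the early value returned −25.0. The direction here comes from the chosen mechanism. The result shows that early values remove this bias when missingness depends on them.

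**5. PET, under the same population line.** The SAP's inputs are mean 35.4, SD 18.1 and a 30% difference: 0.30 × 35.4 = 10.62, and 10.62 / 18.1 = 0.587 SD. Two-sided t-test power is about 83% at n = 50, 79% at n = 45 (10% missing) and 74% at n = 40 (20% missing).

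**The case against.** The strongest reply is that the practical effect is small. The LDL-C result is significant under any plausible loss. Patients unlikely to complete visits are excluded (Protocol section 5.2.i), and lipids are still gathered after unplanned bypass. Section 2.2.a also counts samples taken in the outpatient setting among its comparison samples, so an out-of-hospital draw can serve as the 30-day value and nothing in the SAP bars it. All of this stands. It limits the loss without ending it: the out-of-hospital samples are optional, and patients who withdraw have no further procedures.

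A second reply is that early samples may say little about day 30. Dosing may come up to a week after presentation, some patients leave before day 3, and in-hospital draws are not tied to the dose. This also stands in part. Only values drawn after dosing carry post-dose information. They should inform a model and should not be carried forward as 30-day values.

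A reader might infer that the observed-case analysis overstates the benefit, by supposing that missing evolocumab patients look like placebo patients (an all-randomised difference of 22.5 or 20 points at 10% or 20% missing). The documents do not support that. Treatment is a single dose given by an investigator on the day of enrollment (Protocol sections 4.g and 11), so a patient missing at day 30 has normally had the full dose. Nor does the same dilution belong in the PET power: it would describe a placebo-like imputation with all 50 per arm analysed, not the SAP's analysis.

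**Conclusion.** The point holds as a weakness in the primary estimate, not in its power. The SAP as written gives an observed-case comparison that leaves out randomised patients without a 30-day LDL-C and ignores usable post-dose and baseline information. Power stays above 99.9% with up to 30% missing, assuming the Table 2 means and SDs. The estimate and its interval could be wrong in either direction if missingness differs by arm: by 3, 6 or 9 points at 10%, 20% or 30% missing, given an assumed 30-point difference between missing and observed patients in one arm. With equal shifts and equal rates the bias is zero. Because no missing rate is stated, the actual size is unknown.

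For PET, 10% to 20% missing lowers power for the 30% difference from about 83% to 79% to 74%. A mixed model would not recover this, because only two scans are done. The change is worth making because it is cheap, but the flaw does not invalidate the trial.

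**What to change.** Amend the SAP as follows.

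1. Define the primary population as all randomised participants, analysed by assigned arm. Define evaluable, and align the day window (25–30 days in the protocol, 30 days in the SAP).
2. Analyse LDL-C percent change with a repeated-measures mixed model adjusted for baseline LDL-C. Use every value drawn after dosing, including out-of-hospital samples. Include arm-by-visit terms so that other visits do not force a common effect, and take the 30-day contrast as primary. The same model can carry the time-to-dosing covariate announced in Protocol section 9, which a t-test cannot.
3. Keep the observed-case t-test as a sensitivity analysis.
4. Add a sensitivity analysis that varies missing values in both directions in each arm, rather than assuming placebo-like values after a single administered dose.
5. State how deaths before day 30 are handled. Without such a rule the model estimates a hypothetical 30-day LDL-C for those patients.

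The cost is SAP wording and slightly more programming, with no new data. The model relies on a missing-at-random assumption, which item 4 is there to test.

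### The SAP gives more than 99% power for a 13.5 mg/dL LDL-C difference where the protocol gives 80%, and states it one-sided in mg/dL although the primary test is two-sided on percent change

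*SAP*

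**What the plan says.** The SAP (Primary Endpoint Analysis) defines the endpoint as the between-group difference in mean percent change in LDL-C from baseline to 30 days. On the test it says: "Between-group comparisons will use an independent-samples t-test (two-sample test of means"). On the criterion: "Two-sided p < 0.05 will indicate statistical significance". Its Power Considerations assume a baseline of about 110 mg/dL, a 50% fall on statin and "an additional 50% reduction with evolocumab", and conclude that 50 per group "provides >99% power (one-sided α = 0.05) to detect a 13.5 mg/dL absolute LDL-C difference".

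The protocol (section 9, Sample Size Considerations, Primary endpoints) uses the same 50 per group and the same one-sided 0.05, but reports two separate results. For the planned effect, 55 versus 28 mg/dL at 30 days, "the study has nearly 100% power to detect this difference". For the smaller effect, the trial "will have 80% power to detect an absolute LDL-C reduction of only 13.5 mg/dL (24% reduction in LDL-C at 30 days"). Table 1 repeats the pair: 99+% for the additional 50% lowering, and 13.5 mg/dL in a column headed as detectable at more than 80% power.

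The protocol describes spread in two ways. Table 1 labels the baseline 110 (90-130) as median and IQR, and the prose takes the standard arm "to an LDL-C of 55 (40-70) mg/dL at 30 days" and the evolocumab arm to 28 (14-42), without saying what the 30-day ranges are. Table 2 gives SDs of 14 at baseline, 11 and 10 at 30 days, and 12 and 14 for percent change.

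**The concern.** One difference, one sample size and one alpha cannot carry both 80% and more than 99% power. A reader comparing the two documents cannot tell how sensitive the trial is to a 13.5 mg/dL difference, and cannot work it out, because the SD behind that number is not given.

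The SAP sentence also does not match the analysis it supports. It is the only power statement the SAP makes for its primary endpoint, yet it is one-sided where the test is two-sided, in mg/dL where the endpoint is percent change, and for 13.5 mg/dL where its own premises give about twice that. At stake is the accuracy of a stated design figure.

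**Working it through.** **Method.** Two-sample t-test, n = 50 per arm, df = 98. Noncentrality = Δ / (s√(2/50)) = Δ / (0.2 s), where s is the root mean square of the two arm SDs. Power comes from the noncentral t.

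**1. The SAP's figure, with Table 2's 30-day SDs.** s = √((11² + 10²)/2) = 10.51. At Δ = 13.5 the noncentrality is 13.5 / 2.10 = 6.42, and one-sided power exceeds 99.99%. The SAP's figure reproduces. With these SDs, however, the difference detectable at 80% power is 5.3 mg/dL, so the protocol's 13.5 does not reproduce. (Its 24% is 13.5/55 = 24.5%, which is consistent.)

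**2. Can one SD give both figures?** Solving for s at Δ = 13.5, one-sided 0.05:

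| Power | SD required (mg/dL) |
|---|---|
| 80% | 26.96 |
| 99% | 16.88 or less |

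No. By contrast, the protocol's own pair is coherent: at an SD of 26.96, power is 80% at 13.5 and 99.96% at 27 mg/dL.

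**3. The protocol's ranges read as IQRs.** With SD = width/1.349, which assumes rough normality:

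| | Range | Implied SD | Table 2 SD | Ratio |
|---|---|---|---|---|
| Baseline | 90-130 | 29.65 | 14 | 2.12 |
| 30 days, placebo | 40-70 | 22.24 | 11 | 2.02 |
| 30 days, evolocumab | 14-42 | 20.76 | 10 | 2.08 |

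Only the baseline range is labelled an IQR; reading the other two that way is an assumption. On 30-day values s = 21.51 and one-sided power at 13.5 is 92.9%, so neither stated figure reproduces.

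**4. Change from baseline in mg/dL.** SD of change = √(s₀² + s₁² − 2r s₀s₁). The documents give no correlation r, so a range is shown. One-sided power at 13.5:

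| Assumed r | SDs from ranges as IQRs | Power | SDs from Table 2 | Power |
|---|---|---|---|---|
| 0 | 37.1 / 36.2 | 57.3% | 17.8 / 17.2 | 98.6% |
| 0.2 | – | – | 16.0 / 15.5 | 99.6% |
| 0.4 | 29.1 / 28.6 | 75.1% | – | – |
| 0.5 | 26.7 / 26.4 | 81.1% | 12.8 / 12.5 | 99.99% |
| 0.6 | 24.1 / 23.9 | 87.4% | – | – |
| 0.8 | 17.9 / 18.0 | 98.2% | – | – |

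From the IQRs, 99% is reached only at r of about 0.83. From Table 2 it is reached at about 0.07.

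**5. The effect the SAP sentence describes.** 110 × 0.5 = 55; 55 × 0.5 = 27.5; difference 55 − 27.5 = 27.5 mg/dL.

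**6. The planned test.** Percent change, two-sided 0.05, difference 75 − 50 = 25 points. With SDs 12 and 14, s = √((144 + 196)/2) = 13.04: power exceeds 99.9%, and the difference detectable at 80% is 7.4 points. With both SDs doubled (24 and 28), power at 25 points is 99.7%.

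**The case against.** The best defence is that this is a copying slip, not a dispute about power. The protocol's two results fit a single SD of about 27, and 80% at 13.5 mg/dL can be reached from the ranges printed beside it (81% on change, if r is 0.5). The SAP sentence does not fit its own premises. On this view the SAP joined the protocol's 99+% to its detectable difference, and nothing else is wrong. That is the likeliest explanation, but it remains an inference: the protocol never states an SD of 27, the correlation is assumed, and Table 2's SDs support the SAP's figure over the protocol's.

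It can also be said that Table 1's heading of more than 80% leaves room for more than 99%. The prose says 80% and presents 13.5 mg/dL as a small difference the trial can still detect, so the heading does not remove the conflict.

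Finally, sidedness and scale make no practical difference at the planned effect, the SAP labels its one-sided basis openly, and the two-sided test is the stricter rule. All of that stands. It limits the consequence, but the sentence still describes a different calculation from the planned analysis.

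**Conclusion.** The concern holds, as a minor error in a stated figure. That 80% and more than 99% cannot both be right follows from the t-test alone and needs no assumed SD or correlation. The documents do not settle which is wrong: with Table 2's SDs the protocol's 80% is unsupported; with the ranges read as IQRs the SAP's figure is unsupported on 30-day values, and on change unless r exceeds about 0.83. The mismatch of effect, scale and sidedness within the SAP is plain from its text.

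The trial's adequacy is not affected. Power for the planned 25-point difference is above 99% even with Table 2's percent-change SDs doubled, assuming 50 analysed per arm.

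**What to change.** **SAP.** Replace the power sentence with one matched to the planned analysis, for example: *With 50 evaluable participants per arm and two-sided alpha 0.05, the t-test has more than 99% power for the planned 25-percentage-point difference in mean percent change in LDL-C (SDs 12 and 14).* Take 13.5 mg/dL out of the claim. If reconciling the tables changes those SDs, update them in the sentence; the claim survives a doubling. The sentence makes no allowance for loss to follow-up, so the authors should confirm that 50 per arm is the number they expect to analyse.

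**Protocol, section 9.** State the SD behind 13.5 mg/dL at 80% power, and whether it is an SD of 30-day LDL-C or of change, or recompute the figure. Label the 30-day ranges. Reconcile the baseline IQR and the 30-day ranges with Table 2's SDs. Quote a detectable difference in percentage points only with its SDs (7.4 points at 12 and 14), once Table 2 is settled.

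**Cost.** One sentence in the SAP, and one SD plus range labels and reconciled spreads in the protocol. Sample size, analysis and conduct do not change.
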